The proposed study is a single blind randomized, controlled trial (N=144) with two conditions (4-session BA-PC or TAU) that uses an intent to treat design. Following an initial telephone assessment session, all patients who agree to participate and who meet all inclusion criteria will be asked to participate in the study. As depicted in **Figure 2**, all Veterans will complete a baseline assessment. Eligible Veterans will be randomized in equal proportions to one of two conditions (4-session BA-PC or TAU). All Veterans will complete biweekly brief telephone mood assessments for the first 12 weeks. These brief biweekly assessments can also be completed in-person, if they align with another assessment or if the participant prefers to meet in-person. Comprehensive assessments will occur at 6 weeks and 12 (post-treatment), as well as at 24 weeks. After 12 weeks (post-treatment), all participants will be allowed to seek additional psychological treatment, if desired.

Settings

This study will be implemented in four different primary care clinics in VISN 2 (Syracuse VAMC, Canandaigua, Buffalo VAMC's, and Rochester Outpatient clinic). We will seek Buffalo IRB approval as well.

Study Population

Power analyses revealed that a total of 144 Veterans (72 Veterans per group) will need to be randomized to provide 80% power to detect a medium effect of the intervention on depressive symptoms at the 12-week post-

treatment time point, while accounting for a 30% attrition rate across the 12-weeks. Using the previously collected data to give indication of our screening rates and rates of eligibility and consent to enroll in the trial, we expect to be able to recruit 4-5 eligible patients per month across a 33-month recruitment time period resulting in the ability to recruit approximately 165 Veterans. Ultimately, we would need to conduct telephone screens on approximately 335-379 depending on the specific eligibility (38%-43%) rate used from our preliminary study.

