Baseline Assessment: Veterans: a) reporting at least moderate symptoms of depression, scoring greater than or equal to a 10 on the PHQ-9; b) who are either on a stable antidepressant dose for ≥ 6 weeks or are not taking antidepressants, c) who have been receiving a stable course (i.e., regular scheduled sessions) of outpatient psychotherapy for anxiety disorders, including PTSD, or substance use disorders for ≥ 3 months, and d) who have had no more than one session with the integrated MHP discussing depression as this initial session tends to involve primarily assessment in past 4 weeks (see Relevant Empirical Studies) are eligible.

Exclusion Criteria

Initial Eligibility Screening: Veterans: a) unable to demonstrate an understanding of the informed consent by not being able to answer 5 comprehension questions; b) non-English speaking; and c) who are currently engaged in psychotherapy targeting depressive symptoms are ineligible.

Baseline Assessment: Veterans who: a) are reporting imminent risk of suicide, as evidenced by the suicide assessment identifying the Veteran as imminent risk and in need of intensive treatment, such as hospitalization, b) have an unstable psychiatric condition (e.g., active psychosis or current mania) or who have a history of Bipolar I or II disorder and are in need of more intensive treatment; c) have recently started antidepressants or have not reached a stable dose (< 6 weeks); d) are currently receiving or currently completed (< 1 month) inpatient or intensive outpatient (e.g., partial hospitalization) programs for a mental health disorder and therefore currently engaged in significant mental health treatment likely targeting changes in mood symptoms; and e) who have recently started psychotherapy for an anxiety disorder or substance use disorder (< 3 months) are ineligible.

Procedure

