All participants will be asked about depressive symptoms every two weeks for the first 12 weeks over the telephone or in-person. Participants will also be asked to complete more comprehensive telephone and in-person follow-up assessments at 6, 12, and 24 weeks (as shown in Figure 1 and Table 1). During these assessments, participants will be asked to complete the same questionnaires as during the baseline assessment and several additional measures dependent on the assessment as identified in Table 1 focused on patient receptivity and medication/treatment history.

All assessment sessions will be led by research assistants blind to condition and take place primarily (unless requested otherwise) via the telephone except the baseline, 12, and 24 weeks (see Table 1). The 12-week assessment will occur over the telephone if unexpected circumstances prevents the Veteran from being able to come in to the medical center. All research assistants will track any non-study care given to participants as that may be a potential confounding variable to our examination of treatment effect⁸⁸.

At baseline, 12, and 24 week sessions, information will be collected from the medical chart of each participant regarding his/her current medical problem list, medications, engagement with mental health care, including types of interventions that they may or may not have participated in during the study as monitored by the VA electronic medical record system.

Treatment As Usual Condition

TAU will involve the Veteran receiving an appointment with the integrated MHP at their primary care clinic. At this encounter, the MHP can choose to deliver whatever interventions they deem necessary. In addition, the MHP and Veteran can work together to identify whether and when they would like to meet again during the 12-week period of the active portion of the study. As recommended by Freeland et al⁸⁸, it is unnecessary to force the TAU condition to have the same amount of attention unless the purpose is to examine specific and nonspecific effects, which is not the case in this study.

BA-PC Intervention

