The *Client Satisfaction Questionnaire (CSQ)*¹⁰⁹ is an 8-item self-report questionnaire developed to assess patient satisfaction with medical and mental health treatment on a 1 to 4 Likert scale, with higher scores related to a higher level of satisfaction. For example, Veterans will be asked “How would you rate the quality of service you received?” on a four point scale ranging from poor (1) to excellent (4). Using the anchor points of the scale, each item needs to be rated a 3 or 4, yielding a total score of at least 24 or above to demonstrate a good level of satisfaction. The scale has a high degree of internal consistency and correlates highly with therapists’ ratings of perceived client satisfaction¹⁰⁹. Each item rating and the total CSQ score will be used to evaluate participants' satisfaction with the service (i.e., 4-session PC-BA and TAU).

The BA Acceptability Interview is an 18-item interview that was designed for this study to assess the Veteran’s satisfaction with the specific components of the BA-PC intervention (including the patient education handouts), the acceptability of the intervention, and importance of each element of the intervention to the Veteran on a Likert scale. Open-ended questions will be used to elucidate additional comments about each Likert-scaled item. Veterans will also be asked to comment on the format of the intervention (i.e., length and number of sessions) and modality (in-person, internet, or telephone) for the primary care setting (see Appendix 5). This measure will be administered by the research assistant delivering the intervention at the last BA-PC session (to allow the assessment research assistant to stay blind to condition). It will be used to give us additional information on the acceptability of each component of the BA-PC intervention and collect information on future implementation.

Treatment Engagement will be assessed using two variables collected via CPRS record review and supplemented by the Treatment History questionnaire: 1) number of BA-PC and TAU sessions will be summarized (both conditions will likely have a similar upper limit as BA-PC will optimally provide 4 sessions and research on TAU suggests for those patients seen after an initial visit, the average number of sessions is 3) and 2) whether or not the participant had engaged in specialty care as assessed at week 24.

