While eligibility criteria require a stable history of depressive medication use or non-use, patients may change (drop, add) medications during the twelve week study period. While randomization should equalize patient characteristics between groups and other research has found it has no effect on the relationship between BA and changes in depressive symptoms^{74, 79}, medication change during the course of the trial will be assessed and if necessary it can be examined as a time-varying variable. If a sufficient number of patients are on two or more medications during the course of this trial, we will assess the association (i.e. linear vs. nominal) between the number of medications and depressive symptoms using the likelihood ratio test. Then, the number of depressive medications (in stacked format) will be entered into our model primarily to adjust the other coefficients (time, time*group) for the potential confounding effect on the rate of change in depressive symptoms between groups, due to medication.

Aim 1 (b): To evaluate the efficacy of a 4-session BA-PC in improving other secondary subjective outcomes compared to TAU. Similar to our primary depression outcome, secondary outcomes (i.e., sleep, quality of life, level of environmental reward from experiences) measured at baseline, week 6, and 12 will be analyzed by forming a MLM.

Aim 1 (c): To evaluate a higher level of treatment engagement. For the number of treatment sessions completed, non-parametric methods, such as Kolmogorov-Smirnov, will be used to examine differences between BA-PC and TAU conditions. For those participants continuing to experience moderate-severe symptoms at week 12, we will use chi-square techniques to examine rates of engagement in specialty care using data collected at 24 weeks.

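### Aim 1(c) compares specialty-care engagement only among participants still symptomatic at week 12, with no all-randomised comparison beside it; the example test for session counts also suits the aim poorly

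*Combined protocol and SAP*

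**What the plan says.** The plan for Aim 1(c) is in Data Analysis and Statistical Considerations and has two parts.

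- **Session counts:** "non-parametric methods, such as Kolmogorov-Smirnov, will be used to examine differences between BA-PC and TAU conditions". No subset is imposed, and no effect measure or sidedness is given.
- **Specialty care, from 24-week data:** "For those participants continuing to experience moderate-severe symptoms at week 12, we will use chi-square techniques to examine rates of engagement in specialty care". This is the only specialty-care comparison in the document. Aim 1(c) states no PHQ-9 cut-off for the subset. I read it as 10 or above, in line with the inclusion criterion ("reporting at least moderate symptoms of depression, scoring greater than or equal to a 10 on the PHQ-9") and the PHQ-9 description under Measures.

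Other sections bear on this:

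- Measures, Treatment Engagement, defines the specialty-care variable without a subset: "whether or not the participant had engaged in specialty care as assessed at week 24". It also says that session numbers will be summarised, without naming a statistic.
- Assessments: "At baseline, 12, and 24 week sessions, information will be collected from the medical chart of each participant". The chart items include engagement with mental health care.
- Design Overview: "After 12 weeks (post-treatment), all participants will be allowed to seek additional psychological treatment, if desired". The same section describes a trial "that uses an intent to treat design".
- Study Population sizes the trial at 72 per arm, "while accounting for a 30% attrition rate across the 12-weeks".
- The Background, on the role of integrated services, hopes that Veterans better served in specialty care will accept referral after a brief intervention, with the integrated provider as a bridge.

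**The concern.** Randomisation makes the two arms comparable at baseline. It does not make the week-12 symptomatic subsets comparable if treatment changes who is in them. If BA-PC works, fewer of its participants remain at PHQ-9 of 10 or above, and those who do are on average harder cases than their TAU counterparts. If underlying severity also influences whether someone takes up specialty care, uptake in the two subsets can differ even when BA-PC has no effect on uptake. The direction depends on whether severe patients are more or less likely to engage, which is not known in advance.

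Participants without a week-12 PHQ-9 cannot be classified, so they drop out of this analysis. The Note on Missing Data describes the mixed model and offers no rule for this chi-square.

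For session counts, the aim is directional (a higher level of engagement), but a two-sample Kolmogorov-Smirnov test responds to any difference in distribution. The schedules make a difference in shape possible: BA-PC has four planned sessions, whereas in TAU the provider and Veteran choose whether and when to meet again. A significant result could reflect spread rather than more sessions.

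**Working it through.** The plan gives no figure for Aim 1(c) to reproduce. From the documents I take 72 per arm, 30% attrition, a PHQ-9 threshold of 10 and four planned BA-PC sessions. All uptake rates, symptomatic proportions and session distributions below are **assumptions**, because the documents give none.

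**1. Numbers available.** Retained per arm: 0.70 × 72 = 50.4, about 50. Lost: 0.30 × 72 = 21.6 per arm, or 0.30 × 144 = 43.2 in total, if all planned attrition means a missing week-12 score. Assume 50% of TAU are still symptomatic. A BA-PC effect of d = 0.5 leaves 1 − Φ(0.5) = 31% symptomatic, and d = 0.3 leaves 1 − Φ(0.3) = 38%. With d = 0.5 the subset is 0.50 × 50 = 25 TAU against 0.31 × 50 = 15.5, about 16, BA-PC.

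**2. Bias with no true effect on uptake.** Simulation with 1,000,000 per arm:
- the week-12 score correlates 0.5 or 0.7 with latent severity;
- d = 0.3 or 0.5 on the week-12 score;
- uptake log-odds = −0.5 + slope × severity, with slopes ±0.3, ±0.5, ±0.8 and ±1.2 per SD.

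Over the 2 × 2 × 8 = 32 scenarios the false difference in the subset (BA-PC minus TAU) runs from −4.9 to about +6 points, with a median absolute value of about 2. The extremes need the steepest slope, correlation 0.7 and d = 0.5. The chi-square rejects in 4.9% to 7.2% of trials at a nominal 5%. Over all randomised participants the difference is zero by construction.

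**3. Precision.** 95% half-width at 50% uptake, 1.96 × √[0.25 × (1/n₁ + 1/n₂)]:

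| Comparison | n per arm | Half-width |
|---|---|---|
| Symptomatic subset | 25 v 16 | 31 points |
| All randomised, 30% missing | 50 v 50 | 20 points |
| All randomised, complete | 72 v 72 | 16 points |

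**4. Power** (two-sided 5%).
- *General effect, 30% v 50% uptake:* all randomised 53% (50 per arm) to 69% (72 per arm); subset 25%.
- *Effect confined to the subset, 40% v 60%, with uptake q among the others:* the overall TAU rate is 0.50 × 0.40 + 0.50q and the BA-PC rate is 0.31 × 0.60 + 0.69q. At q = 0.10 this is 25.0% v 25.5%; at q = 0.27 it is 33.5% v 37.2%. Power is 5% to 8% in all randomised, against about 23% in the subset.

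**5. Session counts** (72 per arm, counts 0 to 4, 4,000 to 5,000 simulations, asymptotic Kolmogorov-Smirnov).

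| Assumed distributions | K-S | Rank-sum | Mean difference (Welch) |
|---|---|---|---|
| Identical | 1.0–1.6% | about 5% | about 5% |
| Equal means, mildly different shapes | 5% | about 5% | about 5% |
| Equal means, moderately different shapes | 31% | about 7% | about 5% |
| True shift, mean 2.15 v 2.50 | 20–23% | 37–40% | 37–40% |

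The moderate case uses proportions for 0 to 4 sessions of .06/.19/.36/.27/.12 (TAU) and .20/.15/.17/.21/.27 (BA-PC), both with mean 2.20. With 50 per arm its K-S rejection falls to about 12–13%.

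**The case against.** The subset is arguably the right clinical question. The bridge to specialty care matters for people who still need it, and if BA-PC works, equal or lower overall uptake could be a success. Step 4 bears this out: an effect confined to those still symptomatic would be almost invisible in an all-randomised comparison. This stands, and it is why the subset should stay. It does not explain why nothing is planned beside it.

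A reader might infer three stronger things that the documents do not support.

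- **That the subset analysis breaches intent to treat.** The Design Overview uses the phrase for the trial as a whole, but Data Analysis ties it to the primary analysis and defines it as analysis by assigned group regardless of treatment received. Aim 1(c) is not the primary analysis, and comparing arms within the subset keeps assigned groups. The Treatment Engagement and Assessments sections define a variable and its collection, not an analysis population, so there is no contradiction.
- **That the subset result would be seriously biased.** A bias of about 2 points is small beside a half-width of 31.
- **That the plan commits to a misleading session test.** The wording offers Kolmogorov-Smirnov as an example, so a rank-sum test is already allowed, and session numbers will be summarised anyway. K-S rejection rates of 81% and 97% at equal means can be produced, but only with a U-shaped BA-PC arm (22–25% with no sessions, 33–36% with four) against a sharply peaked TAU arm. Nothing in the documents points to such shapes.

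Finally, the 43 missing week-12 scores treat the whole planning allowance as missing PHQ-9. The 72-per-arm figures assume chart data on everyone; the chart review is tied to the assessment sessions, so its availability for dropouts is not assured.

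**Conclusion.** The point holds as a gap in a secondary aim. The only planned specialty-care comparison conditions on a post-randomisation state and excludes those without a week-12 score, it carries no caveat to that effect, and no all-randomised comparison accompanies it. The likely bias is modest, of either sign, and well inside the noise of a subset of roughly 25 v 16. These sizes rest on assumed uptake, severity and symptomatic rates; the structural point does not.

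The session-count point is minor. On tied counts of 0 to 4, Kolmogorov-Smirnov is conservative, loses power for a shift and can reject on spread alone, so it is a poor basis for a claim of more sessions. How far it could mislead depends on session distributions that the documents do not give.

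This is a cheap improvement to consider. The primary PHQ-9 analysis does not depend on it.

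**What to change.** 1. Add to Aim 1(c) a comparison of week-24 specialty-care engagement by arm in all randomised participants with available data (chart review, supplemented by the treatment history questionnaire), as a risk difference with 95% CI.
2. Keep the week-12 symptomatic subset, labelled descriptive and non-randomised. State the PHQ-9 cut-off, give rates with 95% CIs by arm, and report by arm how many have no week-12 score.
3. For session counts, report the mean difference with 95% CI as the basis for any claim of more sessions. A tie-corrected rank-sum test is optional, since it also reacts somewhat to shape.

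The cost is a few lines of SAP text and no new data collection. The drawback is that all-randomised uptake mixes need for care with engagement and has little power if the effect is confined to those still symptomatic, so both results should be shown together. The chart may also miss non-VA care in people who do not complete the week-24 questionnaire, which should be stated as a limitation.

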Therapeutic Alliance will be assessed using the Working Alliance Inventory (WAI)¹²⁹. The WAI is a 12-item self-report measure that assesses three different domains of the therapeutic alliance, including agreement on therapeutic tasks, agreement on goals of therapy, and development of a therapeutic bond.

Table 1. Schedule of Assessment Measures

SUBJECTIVE ASSESSMENTS	Time (weeks)							
	0	2	4	6	8	10	12	24
	P	T	T	T	T	T	P	T
1. Symptoms of Depression								
a. PHQ-9*	X	X	X	X	X	X	X	X
2. Intensity of Suicidal Ideation								
a. SSI	X			X			X	X
3. Quality of Life								
a. SF-12	X			X			X	X
b. QLI	X			X			X	X
4. Insomnia Severity								
a. ISI	X			X			X	X
5. Symptoms of PTSD								
a. PTSD-CL	X			X			X	X
6. Symptoms of Anxiety								
a. GAD-7	X			X			X	X
7. Level of Reward/Positive Affect from Experiences								
a. EROS	X			X			X	X
8. Pain								
a. Brief Pain Inventory	X			X			X	X
9. Patient Adherence**								
10. Treatment Receptivity								
a. Client Satisfaction Questionnaire				X			X	

b. BA Acceptability Interview***	X
11. Therapeutic Alliance	X
a. WAI	X
12. Mental Health Treatment	
a. Medication and Treatment History Questionnaire*	X X
c. Medication and Treatment via CPRS*	X X
13. Tobacco Use	
a. Tobacco Use Questionnaire	X

Note. P=in person assessment; T=telephone assessment

*These measures are also given in the initial telephone screening assessment.

**This is calculated after session 2, 3, and 4 of BA-PC

***This measure will be administered at the last BA-PC session and sealed in an envelope to allow for confidentiality and for other research staff to stay blind to condition.

Data Analysis and Statistical Considerations

The data analytic strategy emanates from the primary aim and is in line with the method used to estimate the sample size necessary to adequately test the primary hypothesis. Initial analyses will be conducted using a series of 2 (Condition: TAU vs. BA-PC) vs. 2 (Time: baseline, week 12) repeated measures ANOVAs. The primary analysis will be conducted using the intent-to-treat approach; participants who are randomized will be analyzed according to their assigned group regardless of amount of treatment received. The data will be screened for missing cases, outlier scores, and non-normal response distributions. Assumptions underlying statistical models will be assessed by examining standardized residuals, influence diagnostics and homogeneity of variance (e.g. among groups).

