Aim 1 (a, d): To evaluate the efficacy of a BA-PC in reducing depressive symptoms compared to TAU.

MLM will be used to test the primary null hypothesis that no differences exist in the rate of change in depressive symptoms measured by the PHQ-9 between BA-PC and TAU against the two-sided alternative that differences do exist. A composite equation consisting of within and between person effects will be used to analyze our data. The within-person (level 1) equation estimates participants' unique intercept (time=0) and outcome trajectory. The between-person (level 2) equation estimates the average initial status (e.g., week 0 PHQ-9 total score) and rate of change in the primary outcome (e.g., PHQ-9 total score). If the alternative hypothesis is confirmed, there would be a significant cross-level interaction between group and time of assessment suggesting a greater rate of improvement across time among participants randomized to BA-PC condition relative to TAU.

Below is the multi-level composite equation that will be utilized to model depressive symptom severity. The true depression score for the i^{th} person at the j^{th} time point is a linear combination of a between-subject main effect for group, a main effect for time, and a cross-level interaction term between group and time allowing for the fixed effect slope estimate to vary between groups. Random effects include an intercept and slope. Both level-1 and 2 (subject) residuals are assumed to be normally distributed.

$$Dep_{ij} = \underbrace{\gamma_{00} + \gamma_{01}Group_i + \gamma_{10}Time_{ij} + \gamma_{11}Group_i * Time_{ij}}_{Fixed} + \underbrace{\mu_{oi} + \mu_{li}Time_{ij}}_{Random} + \varepsilon_{ij}$$

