Our composite equation assumes a linear trajectory across time, based on our hypothesis of maintaining steady improvement in depression severity throughout the 12-week study period. This assumption may not be true given the timing and number of BA-PC sessions. We propose two alternative theory-driven models to capture an immediate effect from BA and possibly an effect that may weaken during subsequent weeks. Exploratory graphical methods such as subject specific outcome trajectory plots and transformations will be used to assess the linearity (or lack thereof) across time. Non-constant trajectories such as a quadratic time effect and piecewise-linear (PWL) models will be explored to determine the most parsimonious model. Since a linear time model is nested within a quadratic, the likelihood ratio (difference in -2log-likelihood) test can be used to test model fit. In the case where a quadratic provides a better fit than a linear model, consideration will be given to the magnitude of the quadratic effect as well as parsimony. Since a constant rate of change model is not nested within the PWL model, log-likelihoods cannot be compared to assess model fit. However, the Akaike Information Criterion (AIC) statistic (-2LL + 2*# of parameters) can be used to assess fit among non-

nested models. Below is a composite equation that includes two time segments (TS1, TS2) as well as cross-level interactions between time segment and group.

$$Dep_{ij} = \underbrace{\gamma_{00} + \gamma_{01}Group_i + \gamma_{10}TS1_{ij} + \gamma_{20}TS2_{ij} + \gamma_{11}Group_i * TS1_{ij} + \gamma_{21}Group_i * TS2_{ij}}_{\text{Fixed}} + \underbrace{\mu_{oi} + \mu_{1i}TS1_{ij} + \mu_{2i}TS2_{ij} + \varepsilon_{ij}}_{\text{Random}}$$

(d) The above models will be especially useful for assessing sustainability of long-term improvement up to 24 weeks after randomization. An issue of analyzing long-term follow-up data is the rate of “missingness”. Methods described below pertaining to missing data will be inspected and, if plausible, used in conjunction with MLM to compare rates of improvement between the primary 12-week study period and long term follow-up. If the reliability of estimates during the long-term follow-up period are poor due to a high rate of missing data, simple means and confidence intervals will be calculated and used for descriptive purposes.

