Note on Missing Data: One of the advantages of the proposed analytic method is the handling of incomplete outcome data without resorting to listwise deletion of participants. Our analytic method provides unbiased parameter estimates under a missing at random (MAR) assumption. Unfortunately, the validity of MAR cannot be determined from the data. If the MAR assumption does not seem tenable, pattern-mixture models can be used to obtain valid parameter estimates by classifying participants into nominal categories according to the pattern of "missingness"¹¹⁵. This nominal variable is then used as a predictor of the response. The associated regression coefficient and the parameter estimates of its interaction with other predictor variables quantify how the predictor-response association differs across the patterns of missing data. For example, a model consisting of a main effect for time, a main effect for the nominal missing data pattern variable and an interaction term will inform us if baseline depression and depressive symptom trajectories differ according to the type of "missingness". Overall population estimates can be calculated by averaging over the patterns of missing data¹¹⁵ and then statistically compared between groups¹¹⁶. A nice example of using a random-effects pattern-mixture model applied to a two group longitudinal study is shown in Hedeker and Gibbons¹¹⁰.

Patient Safety

Veterans with moderate-severe symptomatology who are eligible to participate in the study may inadvertently delay treatment to remain in the study during the treatment period (12 weeks). As a result, research staff will provide patients a thorough summary of the psychological and pharmacological options for services available to them at the end of the telephone screening session. [name] will assist in linking the Veteran to those services if the patient is interested. At any time during the initial 12-weeks of the study, if the patient indicates interest in seeking psychotherapy, the research staff will immediately help the Veteran with a referral and ask whether the Veteran would consider continuing the assessment portion of the study. In addition, the consent form thoroughly reviews this information.

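### The baseline-to-week-12 ANOVAs are completer analyses as ordinarily run, and the mixed model's MAR claim also needs a correct time curve, which the plan leaves to be chosen after seeing the data

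*Combined protocol and SAP*

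**What the plan says.** **Data Analysis and Statistical Considerations, opening paragraph.** The first analyses named, labelled initial, are "2 (Condition: TAU vs. BA-PC) vs. 2 (Time: baseline, week 12) repeated measures ANOVAs". The paragraph then applies intent to treat to the primary analysis, meaning analysis by assigned group whatever amount of treatment was taken. It gives no rule for a missing week-12 score and does not rank the ANOVAs against the model that follows.

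**Aim 1 (a, d).** The primary test is a mixed model: "MLM will be used to test the primary null hypothesis that no differences exist in the rate of change in depressive symptoms", "against the two-sided alternative that differences do exist". On shape, the plan states "Our composite equation assumes a linear trajectory across time" and then concedes "This assumption may not be true given the timing and number of BA-PC sessions". It continues: "Non-constant trajectories such as a quadratic time effect and piecewise-linear (PWL) models will be explored to determine the most parsimonious model". The quadratic is compared with the line by likelihood ratio, but the size of the quadratic term and parsimony are also weighed. Piecewise models are compared by AIC. No threshold is given.

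**Note on Missing Data.** The stated advantage is the "handling of incomplete outcome data without resorting to listwise deletion of participants", followed by "Our analytic method provides unbiased parameter estimates under a missing at random (MAR) assumption". The note concedes that MAR cannot be checked from the data and offers pattern-mixture models if MAR looks doubtful.

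**Study Population and Design Overview.** 144 Veterans (72 per group) are to be randomized, with power stated for the 12-week time point and 30% attrition. The PHQ-9 is collected every two weeks to week 12.

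**The concern.** There are two separate gaps.

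1. A 2x2 repeated measures ANOVA on baseline and week 12 needs both scores. Run in the ordinary way, it leaves out everyone without a week-12 score and ignores the PHQ-9 values they gave at weeks 2 to 10. It then compares completers only.

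2. Likelihood estimates from a mixed model are protected under MAR only if the mean and covariance models are right. The only condition the Note on Missing Data states is MAR, and its fallback is triggered by doubt about MAR, not by a wrong curve. The choice among line, quadratic and piecewise is left to judgement. The piecewise model has two group-by-time terms, and the plan does not say which contrast would then carry the hypothesis or how the week-12 difference would be formed. That difference, at the time point the trial is powered on, would therefore depend on a choice made from the data.

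**Working it through.** The plan gives no figure for bias or for the participants its ANOVAs would lose, so there is none to reproduce. From the documents: N = 144, 30% attrition, PHQ-9 at weeks 0, 2, ..., 12, and a mixed model linear in time with random intercept and slope. Effect sizes, SDs, bends and dropout strengths below are assumptions.

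**Step 1. Participants the ANOVAs would lose.** 144 × 0.30 = 43.2, so about 43 omitted; 144 × 0.70 = 100.8, so about 101 kept.

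**Step 2. A bent truth, complete data.** Assume the BA-PC minus TAU difference is 0 at week 0, −3.5 at week 4 and −2.5 at week 12, straight in between. At the seven visits it is 0, −1.75, −3.5, −3.25, −3.0, −2.75, −2.5. With complete data and random intercept and slope, the group-by-time estimate equals the least-squares slope through these values.

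- Mean: −16.75 / 7 = −2.39. Sum of squares of weeks centred at 6: 112.
- Cross-product: (−4)(−1.75) + (−2)(−3.5) + (2)(−3.0) + (4)(−2.75) + (6)(−2.5) = 7 + 7 − 6 − 11 − 15 = −18.
- Slope: −18 / 112 = −0.161 per week; over 12 weeks, −1.93.
- Fitted week-12 difference: −2.39 + 6 × (−0.161) = −3.36.

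The line gives −1.93 or −3.36, depending on how it is read, against a true −2.5. This is a shape error and needs no dropout.

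**Step 3. The same bend with MAR dropout.** Large-sample simulation: random-intercept SD 3.5, slope SD 0.2, residual SD 3, dropout depending only on the last observed PHQ-9. With 66% to 74% completing, the 12-week slope difference shifted by 0.24 to 0.37. A repeat gave −1.92 without dropout and −2.16 to −2.36 with it, a shift of 2.16 − 1.92 = 0.24 to 2.36 − 1.92 = 0.44. Week as a category stayed within simulation error of −2.5. With a linear truth, all agreed at about −2.5.

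**Step 4. A second set of assumptions.** Baseline mean 15, random-intercept SD 3, slope SD 0.3 per week, residual SD 3, log-odds of dropout 0.15 per PHQ-9 point (worse scores leave). Week-12 difference in change; 30/30 and 20/40 are percent dropout in TAU/BA-PC:

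| Truth | True | Linear, complete | Linear, 30/30 | Linear, 20/40 | Quadratic, 30/30 | Piecewise, 30/30 |
|---|---|---|---|---|---|---|
| Linear | −2.50 | – | −2.54 | −2.53 | −2.54 | −2.54 |
| BA-PC early, then plateau | −2.50 | −2.47 | −2.80 | −2.92 | −2.53 | −2.54 |
| BA-PC early, then weakens | −1.00 | −1.04 | −1.39 | −1.55 | −1.03 | −1.04 |
| Same bend, no effect | 0.00 | 0.02 | −0.04 | −0.24 | −0.04 | −0.04 |

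Here the line is close to the truth without dropout. In the two middle rows, MAR dropout with the wrong curve puts it off by 0.30 to 0.55.

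**Step 5. The completer ANOVA in the same runs.** With worse scores driving dropout in both arms at 30/30, it was nearly unbiased: −2.51, −2.49 and −1.00 for the first three rows. With dropout in opposite directions by arm and a linear truth of −2.50, it gave −2.32 or −2.74, off by 0.18 and 0.24.

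**Step 6. Would the planned checks find the bend?** At N = 144, the quadratic likelihood-ratio test and the piecewise AIC each flagged the Step 2 bend in 1,000 of 1,000 trials, and each bend in Step 4 in 120 of 120.

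Smaller bends: a straight line to −2.5 at week 12 passes −2.5 × 4/12 = −0.83 at week 4, so the Step 2 bend is −3.5 + 0.83 = −2.67.

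- A quarter of it (week 4 at −0.83 − 0.67 = −1.50): detected 22–25% of the time by the likelihood ratio and about 38–44% by AIC; dropout shifts the slope difference by 0.05 to 0.06.
- At 35% of it: detected 42–67% of the time; shift 0.10 to 0.12.
- The fitted week-12 difference suffers more: off by about 0.25 with week 4 at −1.5, and by about 0.4 with week 4 at −2.0, a bend the likelihood ratio missed in about 43% of trials.

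**The case against.** The strongest reply is that the plan already deals with shape. It says linearity may fail and commits to plots, a quadratic test and piecewise models, and those checks flag a large bend essentially every time. The larger biases above therefore need an analyst to keep a line that every planned check rejects, while bends that can slip through do little harm to the slope. In the Step 2 example most of the error is shape error present in complete data, and dropout moves the slope towards −2.5. The shift is also modest against the estimate's sampling SD of about 0.8 at N = 144. All of this stands, and it limits the size of the point. What it does not answer is that better fit need not change the model, that no week-12 contrast is fixed, and that the MAR sentence omits its second condition.

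A reader might infer that the ANOVAs contradict the plan's own statements on listwise deletion and intent to treat. The documents do not support that. The method praised in the Note on Missing Data is the mixed model, the ANOVAs are labelled initial, and the intent-to-treat sentence concerns assigned group in the primary analysis. Completer analysis is itself inferred from ordinary practice, because the plan states no rule for the ANOVAs.

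**Conclusion.** The point holds as a cheap improvement to a stated analysis. As ordinarily run, the ANOVAs would use about 101 of 144 participants. In the illustrations they are nearly unbiased when worse scores drive dropout in both arms, and off by about 0.2 PHQ-9 points when dropout runs in opposite directions.

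For the mixed model, a large bend left in the line shifts the slope difference by about 0.2 to 0.4 points under MAR dropout in the main illustration, and by up to 0.55 in the second set with unequal dropout. Bends likely to escape the planned checks shift it by about 0.05 to 0.1. These sizes rest on assumed SDs, bends and dropout strengths, none of which the documents give.

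It would go too far to say that the plan has no missing-data protection. With a linear truth the stated model is sound under MAR, and the planned quadratic and piecewise models stayed within about 0.05 of the truth in the second set. The remaining weakness is that the week-12 estimate depends on a curve chosen after seeing the data.

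**What to change.** - Keep the linear mixed model as the test of rate of change.
- Replace the 2x2 ANOVAs with a prespecified mixed model on all observed PHQ-9 scores from weeks 0 to 12, with week as a category, group-by-week terms and unstructured covariance. Report the week-12 difference in change with a 95% CI. If the ANOVAs stay, label them completer-only and supportive.
- In the Note on Missing Data, add that unbiasedness under MAR holds given a correctly specified mean and covariance model.

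The cost is SAP wording and one more model on data already collected. The category model spends more parameters, so its interval is somewhat wider than that of a correct linear model. Seven visits need 7 × 8 / 2 = 28 covariance parameters, so a fallback structure should be named in case the fit fails.
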